## 9.2 Follow-up After Off-Protocol Treatment

REQUIRED STUDIES	Follow-up Prior to Progression a						At Prog	FUP Post-Prog
	3-6 mos after reg (if off-Tx early)	9 mos after reg	End of RT	12 mos after reg	18 mos after reg	24 mos after reg		
History and Targeted Physical Exam b (including weight)	X	X		X	X	X	X	X
Performance Status	X	X		X	X	X	X	X
Disease Assessment				X		X		X
Toxicity Notation c	X	X	X	X	X	X	X	
PRO-CTCAE d	X	X	X	X	X	X	X	
X-RAYS AND SCANS								
PET-CT			(X) h				X	
CT (or MRI) e			X		X			
SPECIMEN SUBMISSION								
FFPE diagnostic tissue f							X	
Peripheral Blood (Streck) f							X	
QOL SUBMISSION g								
PROMIS-Global			X				X	
PROMIS-Fatigue				X			X	
FACT/GOG-Ntx				X			X	

NOTE: Forms are found on the protocol-specific page of the CTSU website ([www.ctsu.org](http://www.ctsu.org)). Forms submission guidelines are found in [Section 14.0](#).

NOTE: Unless indicated otherwise in the protocol, scheduled procedures and assessments (treatment administration, toxicity assessment for continuous treatment, disease assessment, specimen collection and follow-up activities) must follow the established SWOG guidelines as outlined in the SWOG Best Practices document accessible from the "Best Practices" link at: <https://www.swog.org/cclinical-trials/protocol-workbench>.

a Every 3 months (+/- 7 days) for the first year, then every 6 months (+/- 7 days) for the second and third year, then annually (+/-14 days) until 10 years from the date of registration or until time of progression. See also [Section 7.1b](#) for extended allowable windows in event of COVID-19 extenuating circumstance.

b Targeted H&P with systems examined as per the treating physician discretion.

c See [Section 8.6](#) for SAE reporting requirements. Note: If a patient experienced a severe (Grade  $\geq 3$ ) adverse event that is possibly, probably or definitely related to protocol treatment that was not previously reported in RAVE, report SAE on the [S1826 Late Adverse Events Form \(Section 14.4\)](#).

d PRO-CTCAE assessments must be collected within +/- 7 days of timepoints indicated above. **The scheduled follow-up PRO-CTCAE assessments should coincide with the physician-directed toxicity assessment and must be completed even if the patient goes off protocol treatment early for any reason or if a patient is deemed ineligible for any reason until such time that the patient starts a subsequent non-protocol anti-cancer therapy.** See also [Section 7.1b](#) for administration instructions.

e All patients must have a contrast-enhanced CT scan of chest, abdomen and pelvis (+ neck or other involved areas, if involvement at baseline) (or if contra-indicated, CT, MRI, or MR-PET) at 1 and 2 years after registration (+/- 14 days). See also [Section 7.1b](#) for extended allowable windows in event of COVID-19 extenuating circumstance.

f With patient's consent, peripheral blood and tissue must be collected as per [Section 15.2](#).  
**The scheduled follow-up PRO assessments must be completed even if the patient goes off protocol treatment early for any reason or the patient progressed or if a patient is deemed ineligible for any reason.** If a patient refuses or cannot complete the patient questionnaires at any time point, he or she should be asked to do so at the next scheduled assessment time. See also [Sections 14.4](#) for data submission and [15.5](#) for administration instructions.

g Patients who receive Residual PET RT, per [Section 7.5](#), (ONLY) must have a PET-CT (or if contra-indicated, CT, MRI, or MR-PET) within 8-12 weeks after completion of radiation therapy.

## 10.0 CRITERIA FOR EVALUATION AND ENDPOINT ANALYSIS

Response and progression will be evaluated in this study using the revised international working group guidelines (Lugano classification) (101).

### 10.1 Measurement of Treatment/Intervention Effect

#### a. Target Lesions & Target Lymph Nodes

FDG avid lesions: Up to five of the largest dominant nodes, nodal masses, and extranodal lesions selected to be clearly FDG avid. Nodes should preferably be from disparate regions of the body and should include, where applicable, mediastinal and retroperitoneal areas. Non-nodal lesions include those in solid organs (e.g., liver, spleen, kidneys, lungs), GI involvement, cutaneous lesions, or those noted on palpation.

PET 5-Point Scale / Deauville score:

- 1, no FDG uptake above background;
- 2, FDG uptake  $\leq$  mediastinum;
- 3, FDG uptake  $>$  mediastinum but  $\leq$  liver;
- 4, FDG uptake moderately  $>$  liver;
- 5, FDG uptake markedly higher than liver and/or new lesions;
- X, new areas of uptake unlikely to be related to lymphoma.

#### b. Metabolic Response at the end of Cycle 6 or end of treatment.

##### 1. Complete Metabolic Response (CR) (as defined by all the following):

- a. Deauville Score of 1, 2, or 3 with or without a residual mass or nodal lesion:
  - 1, no FDG uptake above background;
  - 2, FDG uptake  $\leq$  mediastinum;
  - 3, FDG uptake  $>$  mediastinum but  $\leq$  liver.
- b. In Waldeyer's ring or extranodal sites with high physiologic uptake or with activation within spleen or marrow (e.g., with chemotherapy or myeloid colony-stimulating factors), uptake may be greater than normal mediastinum and/or liver. In this circumstance, complete metabolic response may be inferred if uptake at sites of initial involvement is no greater than surrounding normal tissue even if the tissue has high physiologic uptake.
- c. No new lesions.
- d. No evidence of FDG avid disease in marrow unless as noted in [Section 10.1b.1b](#).
- e. In the event that a bone marrow biopsy is performed at baseline and the patient had evidence of marrow involvement by bone marrow biopsy at baseline, a repeat marrow will be required to confirm CR. A sample that is negative by immunohistochemistry but that demonstrates a small population of clonal lymphocytes by flow cytometry will be considered a CR.

2. Partial Metabolic Response (PR) (as defined by all the following):
  - a. Deauville Score of 4 or 5 with reduced uptake compared to baseline and residual mass(es) of any size.
  - b. No new lesions.
  - c. In the event that a bone marrow biopsy is performed at baseline: Residual marrow uptake higher than uptake in normal marrow but reduced compared with baseline (diffuse uptake compatible with reactive changes from chemotherapy allowed). If there are persistent focal changes in the marrow in the context of a nodal response, consideration should be given to further evaluation with a BM biopsy.
3. No Metabolic Response (SD) (as defined by all the following):
  - a. Deauville Score 4 or 5 with no significant change in FDG uptake from baseline at interim or end of treatment.
  - b. No new lesions.
  - c. No change in marrow uptake from baseline.
4. Progressive Metabolic Disease (PD) (as defined by any of the following):
  - a. Deauville Score 4 or 5 with an increase in intensity of uptake from baseline.
  - b. New FDG-avid foci consistent with lymphoma.
  - c. New or recurrent FDG-avid foci in the bone marrow.

\* For patients who are contra-indicated for PET-CT, see [Section 18.7](#) for Measurement-based Response Assessment According to the Lugano Classification.

10.2 **Best Response:**

- a. CR: One objective status of CR documented before relapse.
- b. PR: One objective status of PR documented before progression but not qualifying as a CR.
- c. Stable: At least one objective status of stable documented at least 6 weeks after registration, not qualifying as anything else above.
- d. Increasing Disease: Objective status of progression.
- e. Inadequate assessment, response unknown: No other response category applies.

### 10.3 Performance Status

See also [Section 18.4](#).

a. Patients  $\geq 18$  years of age will be graded according to the Zubrod performance status scale:

GRADE	SCALE
0	Fully active; able to carry on all pre-disease activities without restriction.
1	Restricted in physically strenuous activity but ambulatory and able to carry out work of a light or sedentary nature, e.g., light housework, office work.
2	Ambulatory and capable of all self-care but unable to carry out any work activities; up and about more than 50% of waking hours.
3	Capable of only limited self-care; confined to bed or chair more than 50% of waking hours.
4	Completely disabled; cannot carry on any self-care; totally confined to bed or chair.

b. Patients  $\leq 17$  years of age will be graded according to the Lansky play-performance scale for pediatric patients. \*The conversion of the Lansky to Zubrod scale is intended for NCI reporting purposes only. See [Section 18.4](#).

This scale is rated by parents based on their child's activity over the past week. Parents fill out the assessment based on the directions on the form, and the form is re-administered over time to assess for changes in performance status.

An excerpt of the relevant directions for parents is as follows:

"Think about your child's play and activity over the past week. Think about both good days and bad days. Average out this period. Now read the descriptions and pick the one that best describes your child's play during the past week."

RATING	DESCRIPTION
100	Fully active, normal
90	Minor restrictions with strenuous physical activity
80	Active, but gets tired more quickly
70	Both greater restriction of, and less time spent in, active play
60	Up and around, but minimal active play; keeps busy with quieter activities
50	Lying around much of the day, but gets dressed; no active play; participates in all quiet play and activities
40	Mostly in bed; participates in quiet activities
30	Stuck in bed; needs help even for quiet play
20	Often sleeping; play is entirely limited to very passive activities
10	Does not play nor get out of bed
0	Unresponsive

#### 10.4 **Progression Free Survival (PFS)**

From date of registration to date of first observation of progressive disease according to the 2014 Lugano classification, or death due to any cause. Patients last known to be alive and without report of progression are censored at date of last contact. See [Sections 10.1b.4](#) and [18.7](#) for definition of progressive disease according to 2014 Lugano classification.

#### 10.5 **Event Free Survival (EFS)**

From date of registration to date of first occurrence of EFS event. Patients last known to be alive and without EFS event are censored at date of last contact.

EFS Events are defined as:

- Disease progression/relapse
- Administration of non-protocol specified systemic anti-lymphoma therapy (i.e. salvage therapy) at any time after initiation of protocol therapy.
  - Administration of non-protocol specified systemic anti-lymphoma therapy for residual or relapsed Hodgkin lymphoma (whether or not confirmed by biopsy) in the absence of formal progression of disease according to the Lugano classification
- Administration of any non-protocol specified radiation therapy at any time after initiation of protocol therapy:
  - Administration of radiation therapy in a patient who was not declared eligible for radiation therapy at registration
  - Administration of radiation in a patient who was declared eligible for radiation therapy but does not meet protocol-specified criteria for use of radiation (refer to [Section 7.5](#)).

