**7.10 Follow-Up Period**

All patients will be followed until death or 10 years after registration, whichever occurs first.

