### 11.3 Analysis of Secondary Endpoints

Secondary endpoints include overall survival (OS), event-free survival (EFS), metabolic complete response (CR) rate, safety and tolerability.

A key secondary endpoint for the study is OS. Based on previous data, the estimated 2-year OS in the control arm (Arm 2) was 96%. We assume that overall survival in the experimental arm (Arm 1) will follow an exponential distribution, with 4 years of accrual, 2 additional years of follow-up, a stratified log-rank test at two-sided alpha level of .05 will have 90% power to detect a hazard ratio of 2.8 (corresponds to an improvement of OS from 96% in the control arm (Arm 2) to 98.5% in the experimental arm (Arm 1)). A total of 61 OS events (deaths) are required for the final analysis.

Event free survival (EFS) will be estimated using Kaplan-Meier method and compared between treatment arms using cox regression model. Based on the estimated 2-year modified PFS of 82% in the control arm (Arm 2), and the average hazard ratio 1.54, we anticipate at least 195 events under the alternative hypothesis. With 940 eligible patients, the hazard ratio can be estimated to within  $\pm 0.28$  (95% confidence).

Metabolic complete response is defined using 2014 Lugano classification. In the previous study, the CR rate was 86% at the end of frontline therapy for BV-AVD, but the estimate might include BEACOPP and/or radiation therapy. We assume that the CR rate is 83% for BV-AVD alone, with 940 eligible patients, a binomial test at one-sided alpha level of .025 will have 92% power to detect an increase in CR rate from 83% in the control arm (Arm 2) to 90% in the experimental arm (Arm 1).

Toxicity will be evaluated using the CTCAE Version 5 items. Eligible patients receiving at least one dose of drug will be included in the assessment of adverse events by treatment arms. The maximum Grade for each toxicity will be recorded for each patient, and frequency tables will be reviewed to determine toxicity patterns. With 470 eligible patients in each arm, any toxicity with at least 4% prevalence has at least a 90% chance of occurring within an arm. Toxicity rates in each arm can be estimated to within at least  $\pm 4.5\%$  with 95% confidence. Treatment-related toxicities between arms will be compared using Fisher's exact test stratified by age groups.

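### The EFS radiotherapy event has no indication limit, so non-protocol radiotherapy for a second cancer or a benign condition counts as an event, although chemotherapy for the same cancer does not

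*Combined protocol and SAP*

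**What the plan says.** Section 10.5 lists progression or relapse and two treatment-based EFS events.

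- **Systemic therapy:** "Administration of non-protocol specified systemic anti-lymphoma therapy (i.e. salvage therapy) at any time after initiation of protocol therapy". Its sub-bullet refers to treatment for residual or relapsed Hodgkin lymphoma.
- **Radiotherapy:** "Administration of any non-protocol specified radiation therapy at any time after initiation of protocol therapy". It has two sub-bullets. One turns on registration: "Administration of radiation therapy in a patient who was not declared eligible for radiation therapy at registration". The other turns on Section 7.5, to which it points: "Administration of radiation in a patient who was declared eligible for radiation therapy but does not meet protocol-specified criteria for use of radiation".

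Section 18.13d restates the radiotherapy event for the ctDNA analyses, again without an indication. On duration, Section 7.10 says: "All patients will be followed until death or 10 years after registration, whichever occurs first".

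Section 11.3 plans EFS from a two-year control-arm rate of 82%, taken from modified PFS, and an average hazard ratio of 1.54. The event count that follows is put this way: "we anticipate at least 195 events under the alternative hypothesis". The stated precision for the hazard ratio, at 95% confidence and with 940 eligible patients, is ±0.28. Section 2.3 describes the modified PFS of the earlier phase III BV-AVD trial, whose two-year value is about 82%. That endpoint counts later treatment only if it is anti-lymphoma therapy after less than a complete response.

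**The concern.** The two treatment events are built differently. The systemic event asks what the treatment was for. The radiotherapy sub-bullets ask only whether radiotherapy was declared at registration and whether the Section 7.5 criteria were met.

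Take an undeclared adult in remission who develops a solid tumour in year 3. Radiotherapy for that tumour fits the first sub-bullet and is an EFS event; chemotherapy for it is not. The same applies to radiotherapy for a benign condition.

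The protocol allows for such patients:

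- Section 5.2 sets no upper age limit, and Section 6.0 has a stratum above 60 years.
- Section 5.4n admits patients with certain earlier cancers.
- Section 8.6h gives reporting rules for later malignancies.
- Section 14.4n mentions treatment for a second primary.
- Section 11.2 expects radiotherapy almost only in the pediatric group, so most adults are likely to be undeclared and fall under the first sub-bullet.

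EFS is a named secondary objective (Section 1.2b). Events unrelated to lymphoma dilute it. Wording that two analysts could code differently is also undesirable in an open-label trial.

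**Working it through.** **1. Is the limit stated elsewhere?** The two treatment events of Section 10.5, side by side:

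| | Systemic therapy | Radiotherapy |
|---|---|---|
| Header | anti-lymphoma (salvage) only | any that is not protocol-specified |
| Sub-bullets turn on | residual or relapsed Hodgkin lymphoma | declaration at registration; Section 7.5 criteria |
| Indication stated | yes | no |

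Section 18.13d has the same gap, and no other section supplies a limit.

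**2. Reproducing the planned EFS figures.** Section 11.1 gives cure fractions of 70% (control) and 74% (experimental), a hazard ratio of 1.67 among progressing patients, and 940 eligible patients (470 per arm) accrued over 4 years with about 2 more years of follow-up. Section 11.3 gives 82% at two years.

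- Control rate k from 0.70 + 0.30·exp(−2k) = 0.82: k = −ln(0.12/0.30)/2 = 0.458 per year.
- Experimental arm: 0.74 + 0.26·exp(−kt/1.67).
- Expected events, with follow-up u uniform on 2 to 6 years: 470 × mean[1 − S(u)] = 115.1 + 79.3 = 194.5, against 195 in the plan.
- Half-width on the log hazard ratio scale: 1.96 × 2/√195 = 0.281, against ±0.28 in the plan.

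Both figures reproduce. The 82% comes from an endpoint that already counts only anti-lymphoma therapy, so adding the limit leaves them unchanged.

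**3. Time at risk.** Total follow-up is 940 × 4 = 3,760 patient-years, but only time before the first EFS event counts. Event-free time per control patient is 0.70u + 0.30(1 − exp(−ku))/k; the experimental arm uses 0.74, 0.26 and k/1.67. Averaged over u and multiplied by 470, this gives 1,567 + 1,680, or about 3,248 patient-years.

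**4. Size of the dilution.** The documents give neither a second-cancer rate nor an irradiated share. Assumed here: 0.2 to 0.8 second cancers per 100 patient-years, and 20% to 50% irradiated.

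- Low: 3,248 × 0.002 × 0.20 = 1.3 events (0.7% of 195).
- High: 3,248 × 0.008 × 0.50 = 13.0 events (6.7% of 195).

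Splitting 195 events in the ratio 1.54:1 gives 118.2 and 76.8. With x extra events divided equally, HR ≈ (118.2 + x/2)/(76.8 + x/2). This is a crude event-ratio approximation.

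| x | HR | Shift in log HR | Share of ±0.28 |
|---|---|---|---|
| 0 | 1.540 | 0 | 0 |
| 1.3 | 1.536 | 0.003 | 1% |
| 13.0 | 1.498 | 0.028 | 10% |

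For comparison, ±0.28 around 1.54 spans about 1.16 to 2.04.

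**The case against.** The best counter-argument is context. The sub-bullets use the vocabulary of Residual PET radiotherapy: declaration at registration (Section 5.3e) and criteria for residual lymphoma sites (Section 7.5). Section 7.8e draws a similar contrast, and Section 7.2b lists radiation among antineoplastic therapies. Radiotherapy for lymphoma was probably what was meant. That stands as evidence of intent, but the text does not say it, and the neighbouring bullet shows that the limit was written out where wanted.

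A second argument is that a rule blind to the reason for treatment avoids an unblinded judgement. The trial is open-label (Section 7.1a), and Section 11.2 records concern about radiotherapy use in the N-AVD arm. The documents do not give this as a rationale, and it has little force for radiotherapy to a documented second cancer. It does matter where the indication is unclear, and the fix should allow for that.

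Three stronger readings are tempting but unsupported:

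- **All radiotherapy is an event.** It is not; protocol radiotherapy under Section 7.5 is excluded. For a declared patient who met Section 7.5, later radiotherapy for another condition is reached only by the header, not by a sub-bullet.
- **The trial's main conclusion is at risk.** The PFS definition in Section 10.4 does not use this rule.
- **The bias becomes large over ten years.** Such events can accumulate, but the 195 events belong to a horizon of about six years (4 accrual plus 2 follow-up), and the documents give no rate from which to project further.

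**Conclusion.** The point holds as a minor error in a stated rule: as written, it classifies some patients without lymphoma failure as EFS events, and differently from the modified PFS used to plan EFS. No planned figure is wrong.

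On the assumed rates the effect is at most about a tenth of the stated half-width, and that upper end needs both assumptions at their maximum. The direction toward the null rests on the extra events being balanced between arms. The wording gap is certain from the text; its size is not, and is probably small. Benign indications are not included in the estimate, because the documents give no basis for a rate.

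**What to change.** In Sections 10.5 and 18.13d:

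1. Restrict the radiotherapy bullet to non-protocol radiotherapy given *for Hodgkin lymphoma (residual, relapsed or consolidative)*, and keep both sub-bullets.
2. State that radiotherapy for a documented other malignancy or for a benign condition is not an EFS event.
3. State that radiotherapy of unclear indication counts as an event. Event status will now depend on a site-reported reason in an open-label trial, and this default limits the room for judgement.
4. Confirm that the Non-Protocol Therapy Form (Section 14.4m) records the indication. The form is not among the documents, so it may already do so; if not, one field is needed.

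The cost is a few lines of text in two sections and possibly one data field. It needs no extra patients or procedures, and the planned 195 events and ±0.28 stay as they are.

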#### 10.6 **Time to Death**

From date of registration to date of death due to any cause. Patients last known to be alive are censored at date of last contact.

#### 11.2 Interim Analysis

For early reporting, interim analyses will be conducted when 25%, 50% and 75% of anticipated progressions or deaths in the pooled across arms have been observed. This under the alternative hypothesis this approximately corresponds to 58%, 85% of accrual and six months after completing full accrual. Evidence suggesting early termination for of the study would be if the alternative hypothesis of a greater than average hazard ratio control vs. experimental hazard ratio of 1.58 is rejected at a one-sided .5% level at the first interim analysis, and 1% level at second or later of the interim analyses. At the second interim analysis testing would approximately correspond to observing a hazard ratio favoring the control of approximately .96. The conservative first interim analysis acknowledges the potential late therapeutic effect of the experimental arm relative to the control arm. The timing of interim analyses will be based the combined number of PFS events across arms. At full information or the time of primary analysis will occur when 179 PFS events have been observed.

Interim Analysis	Information	One-sided Futility p-value	One-sided superiority P-value
1	25%	.002	NA
2	50%	.01	.005
3	75%	.01	.005

At the second two interim analyses superiority testing will be conducted at the .5% level.

Final Analysis Plan: If the trial is not stopped early, the final analysis will test the null hypothesis ( $HR=1$ ) for PFS using stratified log-rank test with a one-sided alpha of 0.021. The strata used in the stratified log-rank test are those defined and coded as in Section 6.0 in the dynamic balancing randomization scheme utilized for the study. The variables include: Age (years): age 12-17 vs. age 18-60 vs. age > 60, International prognostic score: 0-3 vs. 4-7 and Pre-specified plan to use Residual PET Radiation Therapy (Residual PET RT)\*: yes vs. no. The analysis will be based on modified intent-to-treat and will include all eligible patients as randomized regardless of treatment received. The one-sided alpha of .021 will control of the overall type-one error of the study (including the 2 interim superiority analyses) to be less than .025. The final analysis type-1 error calculations were based simulation studies using the information times specified in the interim analysis schedule and interim analysis specified superiority p-value testing.

RT monitoring: The use of RT will almost exclusively be on the pediatric population, but due to the concern appropriate use in N-AVD arm given the potential of false progressions, it will be monitored closely throughout the study. The DSMB will be provided rates of radiotherapy used in each arm (and within the 12-17 years and  $\geq$  18 years age groups in each arm) for each meeting. The committee will monitor the rate of radiotherapy in both arms and by age group to ensure that there is no overuse in the experimental arm (Arm 1). Due to variability in early event calculations focus on this analysis will not commence until after 30 patients have completed RT. At that point, if there is greater than 15% difference between arms, then the additional communication to NCI and study team for protocol amendment would be considered. This substantive threshold for action in rates is motivated by limited sample sizes and by a slightly higher expected baseline rate of RT use in the N-AVD arm based on the ECHELON-1 and CheckMate 205 studies. If after 75 patients have received RT, then a smaller difference (10%) would be considered a concern and warrant additional discussion with NCI and the study team. We will apply the same rules to RT differences within each age group in each arm.

